7.2. Protocol Deviations

Subject-specific protocol deviations will be summarized by the reason for the deviation, the deviation category, treatment group, and disease severity ([Table 8](#)). A summary of major deviations will also be generated ([Table 9](#)). All subject-specific protocol deviations and non-subject specific protocol deviations will be included in listings ([Listing 3](#) and [Listing 4](#)).

8. EFFICACY EVALUATION

8.1. Primary Efficacy Analysis

8.1.1. Primary Analysis of Time to Recovery

The primary analysis uses the stratified log rank test to compare treatment to control through Day 29 with respect to time to recovery, as defined in Section 3.3. Stratification is based on ordinal scale at baseline (4, 5, or 6). As noted in Section 3.3, all deaths within 29 days will be considered censored at Day 29 with respect to time to recovery. Conceptually, a death corresponds to an infinite time to recovery, but censoring at any time greater than or equal to Day 29 gives the same answer as censoring at Day 29; both correspond to giving deaths the worst rank.

As noted in Section 6.6.3, to maintain an overall two-sided type-I error rate of 0.05, the Lan-DeMets spending function analog of the O'Brien-Fleming boundary will be used to derive the cumulative error spending and boundaries for the interim analysis.

For the final analysis, the log rank test will be performed using the pseudocode provided in Section 6.1. The following pseudocode can be used to compute the bounds for the final analyses and compare to the calculated log-rank statistic. The Boundaries dataset will contain the updated boundaries calculated from the interim analyses using the actual information levels observed at the interim analysis.

```

dataParms_LogR;
  set logrankp(rename=(Statistic=Estimate));
  if Variable='TreatmentVariable';
  _Scale_='Score';
  _Stage_=AnalysisNumber;
  keep Variable _Scale_ _Stage_ StdErr Estimate;
run;

proc seqtest Boundary=Boundaries
 Parms (Testvar=TreatmentVariable)=Parms_LogR
  infoadj=prop
  boundaryscale=score
  ;
  ods output Test=FinalResults ParameterEstimates = LogHRest;
run;

```

If the trial is stopped at the interim analysis, then to derive the p-value, hazard ratio estimate, and confidence interval for the early and final analysis sets, stage-wise ordering of the sample space will be used [5]. The resulting p-value, median unbiased estimate, and confidence interval will be presented in the final report. If the trial is not stopped early, then the fixed sample estimates of the statistics using an alpha level of 5% will be computed and reported for the final analysis. The SAS pseudocode above provides estimates for the log hazard ratio and so the estimates will be exponentiated and reported.

The primary analysis will be performed in the mITT analysis population. The treatment hazard ratio estimate and confidence interval and p-value from the stratified log rank test will be presented (Table 10). The median time to event and 95% confidence interval will be summarized

by treatment arm and disease severity. In addition, stratum-specific estimates of the treatment hazard ratio from Cox models run within each of the disease severity strata will be presented. Kaplan-Meier curves for each treatment arm will be presented, supplemented with the hazard ratio estimate, p-value, and the number of subjects at risk in each arm and severity stratum at Days 1, 3, 5, 8, 11, 15, 22, and 29 ([Figure 3](#)).

Subject listings of the ordinal scale results by day will be generated ([Listing 5](#)).

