3. OBJECTIVES AND ENDPOINTS

The overall objective of the study is to evaluate the clinical efficacy and safety of different investigational therapeutics relative to the control arm among hospitalized adults who have COVID-19.

OBJECTIVES	ENDPOINTS (OUTCOME MEASURES)
Primary	
To evaluate the clinical efficacy of RDV+ interferon beta-1a compared to RDV + placebo, as assessed by time to recovery for patients with baseline ordinal score 4, 5 and 6.
 
Day of recovery is defined as the first day on which the subject satisfies one of the following three categories from the ordinal scale:
 
 • Hospitalized, not requiring supplemental oxygen – no longer requires ongoing medical care; • Not hospitalized, but new or increased limitation on activities and/or new or increased requirement for home oxygen; • Not hospitalized, no limitations on activities. 
Recovery is evaluated up until Day 29 (+ 6 days).

Key Secondary	
To evaluate the clinical efficacy of RDV+ interferon beta-1a compared to RDV + placebo, as assessed by clinical status (8-point
 
 • Death; • Hospitalized, on invasive mechanical ventilation or ECMO;

OBJECTIVES	ENDPOINTS (OUTCOME MEASURES)
ordinal scale) at Day 15 for patients with baseline ordinal score 4 and 5.	
 • Hospitalized, on non-invasive ventilation or high flow oxygen devices; • Hospitalized, requiring supplemental oxygen; • Hospitalized, not requiring supplemental oxygen – requiring ongoing medical care (COVID-19 related or otherwise); • Hospitalized, not requiring supplemental oxygen – no longer requires ongoing medical care; • Not hospitalized, but new or increased limitation on activities and/or new or increased requirement for home oxygen; • Not hospitalized, no limitations on activities.

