Appendix C - ACTT-3: Remdesivir + Interferon Beta-1a

The primary outcome is time to recovery by Day 29. Recovery is defined by discharge from the hospital (i.e., ordinal scale categories 1 or 2) or subject is still hospitalized, but not requiring supplemental oxygen and no longer requires ongoing medical care (category 3). See table above in [Section 3](#) for more details.

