9. STATISTICAL CONSIDERATIONS

9.1 Statistical Hypotheses

The primary hypothesis tests whether the time-to-recovery by Day 29 differs between the experimental and control arms.

Table 6. Hypothesis tests of interest for ACTT-3

ACTT-3	
Primary hypothesis	RDV + interferon-beta-1a versus RDV + placebo

A key secondary hypothesis tests the null distribution of a similar distribution of 8-point ordinal scale at Day 15. For this, the parameter of interest is the “common odds ratio,” which quantifies the shift in the severity distribution resulting from treatment. For an efficacious treatment, an odds ratio greater than 1 quantifies an improvement in disease severity; a value of 2 indicates a bigger improvement than a value of 1.25. The null hypothesis to be tested is that the odds of improvement on the ordinal scale is the same for the control and experimental treatment arms (i.e., the common odds ratio is 1). It is worth noting that, for large sample sizes, the test based on the proportional odds model is nearly the same as the Wilcoxon rank sum test.

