3.2. Endpoints

Primary Endpoint

Time to recovery, where recovery is defined as clinical status in states 1, 2, or 3 of the 8-point ordinal scale, through Day 29 (+6).

- Clinical status of a subject (8-point ordinal scale) is defined below:
 8. Death;
 7. Hospitalized, on invasive mechanical ventilation or ECMO;
 6. Hospitalized, on non-invasive ventilation or high flow oxygen devices;
 5. Hospitalized, requiring supplemental oxygen;
 4. Hospitalized, not requiring supplemental oxygen - requiring ongoing medical care (COVID-19 related or otherwise);
 3. Hospitalized, not requiring supplemental oxygen - no longer requiring ongoing medical care;
 2. Not hospitalized, but new or increased limitation on activities and/or requiring new or increased home oxygen;
 1. Not hospitalized, no limitations on activities

Secondary Endpoints

The key secondary endpoints are:

- Clinical status (8-point ordinal scale) on Day 15.
- Time to recovery, where recovery is defined as clinical status in states 1, 2, or 3 of the 8-point ordinal scale, through Day 29 (+6).

The other secondary endpoints are:

- Ordinal outcome assessed while hospitalized (Days 3, 5, 8, 11) and on Days 15, 22, and 29.
- NEWS assessed daily while hospitalized (Days 3, 5, 8, 11) and on Days 15 and 29.
- Days of supplemental oxygen (if applicable).
- Days of non-invasive ventilation/high-flow oxygen (if applicable).
- Days of invasive mechanical ventilation/ECMO (if applicable).
- Days of hospitalization.
- Date and cause of death (if applicable).
- D-dimer and CRP on Day 1, while hospitalized (Days 3, 5, 8, 11), and on Days 15 and 29.
- SAEs.
- Grade 3 and 4 adverse events

- WBC with differentials, hemoglobin, platelets, creatinine, total bilirubin, ALT, AST, INR, d-dimer, and CRP on Day 1; Days 3, 5, 8, and 11 (while hospitalized); and Days 15 and 29 (if attends in-person visit or still hospitalized).

Exploratory Endpoints (not described in this SAP)

- Qualitative and quantitative polymerase chain reaction PCR for SARS-CoV-2 in OP swab on Day 1; Days 3, 5, 8, and 11 (while hospitalized); and Days 15 and 29 (if attends in-person visit or still hospitalized).
- Deep sequencing of the SARS-CoV-2 virus for those subjects with sustained vial shedding
- Qualitative and quantitative PCR for SARS-CoV-2 in blood on Day 1; Days 3, 5, 8, and 11 (while hospitalized).

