3.3.2. Recovery and Time to Recovery

The primary efficacy and one of the key secondary outcome measures is the time to recovery assessed through Day 29 + 6 days. Recovery will be defined as having a value of 1, 2, or 3 on the clinical status 8-point ordinal scale. The time to recovery will be defined as the elapsed time (in days) from randomization to the earliest day at which a subject reaches recovery. Note that since clinical status assessments are recorded as defined in Section 4.3, the day that is being assessed (not necessarily the day the response is collected) will be used to determine the timing of events. For example, a subject with a score of 5 recorded on Days 1-3 and a score of 3 recorded on

Day 4 will have a time to recovery equal to 3 days. It is also possible that a subject has a clinical status score > 3 reported for a particular day but was subsequently discharged on the same day. Such cases and other special cases will be reviewed by the Endpoint Review Committee or the NIAID Medical Officer, or her designee(s), to make the determination of whether the subject should be considered recovered in analyses. Subject data to be reviewed as part of this determination will include the reported clinical status scores while hospitalized, where the subject was discharged to (e.g. private residence, rehabilitation facility, long-term care/nursing home, comfort and care), and any information regarding readmittance. Subjects discharged to hospice or other end-of-life care will not be considered recovered. Additional information may be solicited to assess recovery.

Any subjects that are lost to follow-up or terminated early prior to an observed recovery will be censored at the day of their last observed assessment. Subjects who complete follow-up but do not experience recovery will be censored at the day of their Day 29 visit. All deaths that occur on or before Day 29 (and prior to any observed recovery) will be considered censored at 28 days. Note that we do not expect many subjects to worsen after discharge. However, we will evaluate whether any discharged subjects subsequently experience a worse clinical status and sensitivity analyses will be conducted accordingly. For these analyses, subjects who recover but are later readmitted for COVID-19 will not be considered a recovery but will instead be censored at 28 days.

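### The SAP and protocol do not settle whether the primary endpoint ends on Day 29 or Day 29 +6, and the SAP's worked example counts one day too many (minor)

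*SAP*

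**What the plan says.** **Day 29 +6.** SAP 3.3.2 defines the outcome as "time to recovery assessed through Day 29 + 6 days", and SAP 3.2 gives the same end. Protocol Appendix C section 3 states "Recovery is evaluated up until Day 29 (+ 6 days".

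**Day 29.** SAP 8.1.1 compares the arms through Day 29. Appendix C 4.1 states "The primary outcome is time to recovery by Day 29", and Appendix C 9.1 "tests whether the time-to-recovery by Day 29 differs between the experimental and control arms". The at-risk counts in SAP 8.1.1 and the summary in SAP Table 17 also stop at Day 29.

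**Censoring in SAP 3.3.2.** For completers: "Subjects who complete follow-up but do not experience recovery will be censored at the day of their Day 29 visit". For deaths: "All deaths that occur on or before Day 29 (and prior to any observed recovery) will be considered censored at 28 days". SAP 6.5 and Appendix C 9.4.2 censor deaths at Day 29 without limiting the rule to deaths by that day.

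**Worst rank.** SAP 8.1.1 adds that "censoring at any time greater than or equal to Day 29 gives the same answer as censoring at Day 29", so that deaths take the worst rank.

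**Day counting.** SAP 3.3.2 counts elapsed days from randomization to the day assessed, not the day the score is collected. SAP 4.3 sets Day 1 at randomization and makes each later score describe the day before. The example in SAP 3.3.2 gives 3 days for a patient whose first recovery score is recorded on Day 4.

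**The concern.** This is the only primary test. Under SAP 6.8 it gates the p-values for the key secondary outcomes and for mortality in baseline scores 4 and 5. The key secondary analysis of time to recovery follows the same rules.

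Two programmers could follow different sections and count different events. If recoveries on Days 30-35 are events, deaths censored at 28 days have already left the risk set. They then no longer rank worst, contrary to the stated intention.

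The worked example is the part of the text a programmer is most likely to copy. Its one-day error would pass straight into the reported medians.

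**Working it through.** **1. Is +6 an analysis horizon or a visit window?** For a window: the Appendix C schedule (1.2) lists 29 + 6 in its window row, and Appendix C 5.6.2 and 8.1.2.1 use the word. Against: SAP 3.2 and 3.3.2 and Appendix C section 3 do not. Appendix C 5.6.2 itself says the endpoint is measured through that window. SAP 8.1.1 takes its endpoint from SAP 3.3. SAP 3.3.2 has no cap, whereas SAP 3.3.10 censors time to death at the earlier of the Day 29 visit and actual Day 29. No sentence excludes a recovery first assessed on Days 30-35.

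**2. The worst-rank sentence.** On the elapsed scale Day 29 is 29 - 1 = 28 and Day 35 is 35 - 1 = 34. An illustration used 462 patients per arm, with assumed deaths (interferon v placebo) and an assumed, equal number of late recoveries per arm:

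| Late recoveries per arm | Deaths | Z, deaths censored at 28 | Z, deaths censored at 34 or later |
|---|---|---|---|
| 0 | 10 v 25 | 0.277 | 0.277 |
| 5 | 10 v 25 | 0.172 | 0.275 |
| 10 | 10 v 25 | 0.048 | 0.274 |
| 10 | 25 v 10 | 0.500 | 0.274 |
| 10 | 18 v 18 | 0.274 | 0.274 |

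With everything capped at Day 29, Z is 0.277 in every row. So the sentence is right when nothing after Day 29 counts. It fails when later recoveries count and deaths are unequal, and the arm with more deaths then gains. These rows show the mechanism, not the likely size, because they fix equal late counts in arms that have unequal numbers still at risk.

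**3. The worked example.** A score recorded on Day 4 describes Day 4 - 1 = Day 3. Elapsed time from Day 1 is 3 - 1 = 2 days. The printed 3 can be reproduced in two ways:
- From the recorded day: 4 - 1 = 3. The text just before the example rules this out.
- As the study-day number of the day assessed. On that scale Day 29 is 29, not 28.

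A uniform shift of one day leaves the ranks, and so the log-rank test, unchanged. Ranks are affected only if recoveries carry study-day numbers while deaths stay at 28 elapsed days. A Day 29 recovery is then coded 29, after the deaths have left the risk set.

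**4. Size.** The planned total reproduces: 831 / 0.90 = 923. The documents give no distribution of visit dates among unrecovered patients, so the cases below are assumptions.
- Assessed on schedule: no late recoveries and no difference.
- Visits on Days 29-30: with the recording lag, a score taken on Day 30 describes Day 29, so again none are late.
- Visits spread evenly over Days 29-35, 90% of all subjects recovering, 5% deaths and the one-day lag: about 5 to 9 late recoveries, or 5/831 = 0.6% to 9/831 = 1.1% of the target.

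For the third case, mean stratified log-rank Z under the rules as written differs from a Day 29 cap by no more than about 0.05. The bound comes from 1000 simulated trials per setting: 462 v 461 patients, assumed mix of baseline scores 4/5/6 of 15/77/8%, relative recovery hazards 2/1/0.4, Weibull shapes 0.85 and 1.2, deaths 5% v 5% or 6% v 2%. That run set 90% recovery among survivors and ignored the lag. It gave 12 to 19 late recoveries and differences of 0.00 to 0.05, so the bound is on the high side for 5 to 9. It is a mean: a single trial can move further, as in the second row of the table (0.277 - 0.172 = 0.105).

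**The case against.** The strongest reply is that +6 is only a visit window. The schedule places it beside the windows for Days 15 and 22, and SAP 8.1.1 names Day 29 as its horizon in the paragraph that contains the worst-rank sentence. On that reading the sentence is correct and only a cap has been left out. This largely stands, and it is why the point is minor. It does not close the gap, because SAP 3.3.2 censors at the actual visit day and nothing excludes later recoveries.

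Second, late visits mainly concern people who have already recovered. Ordinal categories 1 and 2 mean discharged, so an unrecovered completer is normally an inpatient assessed daily, apart from cases such as hospice discharge or transfer. This stands too: visits spread over Days 29-35 are an upper case, and no late recoveries is the more realistic one.

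Third, SAP 6.5, SAP 8.1.1 and Appendix C 9.4.2 place deaths at Day 29. That is 29 under study-day coding, so following the example consistently keeps deaths in last place. This stands, and limits the example's effect to the one-day shift.

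**Conclusion.** A minor inconsistency that should be corrected. The end of the primary endpoint is given in two ways, no cap excludes recoveries first assessed on Days 30-35, and the example is one day too long by the SAP's own rules.

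A reader might infer that the worst-rank sentence in SAP 8.1.1 is false, or that the primary test is biased towards the arm with more deaths. The documents do not support either. The sentence is true for the horizon that section states, and any effect needs late recoveries that scheduled assessment of inpatients would largely prevent. A reader might also infer that the example by itself destroys the ranking of deaths; that needs mixed day coding, which no section prescribes.

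The one certain numerical consequence is that coding recoveries as in the example adds one day to every reported median in both arms. The size given for the test rests on the assumed visit dates, death rates and recovery distribution. In the simulations no mean Z crossed 1.96 between rules.

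**What to change.** - In SAP 3.2, 3.3.2, 3.3.4 and 8.1.1 and protocol Appendix C section 3, state that +6 is a visit window only and that the analysis ends at actual Day 29 (28 elapsed days). SAP 3.3.4 is included because time to improvement uses the same censoring rules.
- Censor unrecovered completers, and all deaths before recovery, at 28. The sentence in SAP 8.1.1 is then true as it stands, and the rule matches SAP 3.3.10.
- Define time to recovery as the study day assessed minus 1, and correct the example to 2 days.
- Align Appendix C 8.1.2.2, which ends daily collection at Day 29, with 8.1.2.1, which continues into the window. The score that describes Day 29 is recorded on Day 30 and has to be collected.

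The cost is a few sentences in each document. The downside is that recoveries first assessed on Days 30-35 are not counted: none under scheduled assessment, and about 5 to 9 in the spread-visit case.

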9.4.7.2 Interim Efficacy Review

The Lan-DeMets spending function analog of the O'Brien-Fleming boundaries will be used to monitor the primary endpoint as a guide for the DSMB for an overall two-sided type-I error rate of 0.05. Interim efficacy analyses will be conducted at approximately 50% and 100% of total information.

Conditional power will be presented as an additional guide to the DSMB. Conditional power allows computation of the probability of obtaining a statistically significant result by the end of the trial given the data accumulated thus far, incorporating and assuming a hypothesized treatment effect (e.g., the treatment effect assumed for sample size determination) thereafter. If conditional power is less than 20% under the original trial assumptions, consideration should be given to stopping the trial.

The unblinded statistical team will prepare these closed reports for DSMB review and recommendations. Analyses will be presented with blinded codes for treatment arms to protect against the possibility that the DSMB report may fall into the wrong hands. A DSMB charter will further describe procedures and membership.

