6. GENERAL STATISTICAL CONSIDERATIONS

6.1. General Principles

This is a double-blind, placebo controlled randomized trial with a two-sided type I error rate of 0.05. Secondary hypotheses have been ordered according to relative importance. These will be described according to the appropriate summary statistics, e.g.:

- Percentages/proportions/odds ratios for categorical data. For tabular summaries of percentages/proportions, the denominator (e.g. number of subjects with non-missing data) will be displayed.
- Means, median, and range for continuous data, median for time-to-event data.

Confidence intervals will be generated; for the primary analysis, the confidence level will take into account the group-sequential design of the trial (see Section 6.6 and Section 8.1) whereas 95% confidence intervals will be generated for secondary and exploratory outcomes. For hazard ratio and odds ratio estimates, Wald confidence intervals will be used. For other efficacy outcomes (e.g. proportions), Wilson or Score confidence intervals will be used. For safety outcomes, exact (e.g., Clopper-Pearson) confidence intervals will be used.

When calculating treatment effects (e.g., differences, hazard ratios, odds ratios) and when using treatment arm as a covariate in regression modeling, the placebo + remdesivir arm will be used as the reference group. For regression modeling that uses strata variables defined in Section 6.4, the first stratum listed for each variable in that section will be used as the reference group.

For the final time-to-event analyses, the following SAS pseudocode will be used to perform stratified analyses to generate stratum-specific median time to event estimates and confidence intervals, stratum-specific Kaplan-Meier curves, and to perform the log-rank test. For any unstratified analyses, code can be used after the removal of the `strata ... ;` line.

```
proc lifetest data=dataset plots=(s);
  time TimeVariable * CensorVariable(1);
  strata StrataVariable;
  test TreatmentVariable;
run;
```

Note that the interim efficacy analyses will be performed using R. For all interim and final analyses, the software used will calculate the log rank statistic using the formula in Section 8.1.1.

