6.6.3. Interim Efficacy Review

An interim efficacy analysis will be conducted after approximately 50% of total information has been reached. The information fraction at an interim analysis will be computed as $t = r/723$ where r is the number of recoveries by the time of the data freeze date for the interim analysis. The Lan-DeMets spending function analog of the O'Brien-Fleming boundary will be used to monitor the primary endpoint using an overall two-sided type-I error rate of 0.05. Specifically, two one sided boundaries are constructed at level 0.025 using the spending function

$$\alpha^*(t) = 2[1 - \Phi\{2.241/t^{\frac{1}{2}}\}],$$

where Φ is the standard normal distribution function. Lan-DeMets software from the University of Wisconsin, now available in the R package 'ldbounds', will be used to calculate boundaries.

Conditional power will be presented as an additional guide to the DSMB. Conditional power allows computation of the probability of obtaining a statistically significant result by the end of the trial given the data accumulated thus far, incorporating and assuming a hypothesized treatment effect (e.g., the treatment effect assumed for sample size determination) thereafter. If conditional power is less than 20% under the original trial assumptions, consideration should be given to stopping the trial.

The unblinded statistical team will prepare these closed session reports for DSMB review and recommendations. Analyses will be presented with blinded codes for treatment arms to protect against the possibility that the DSMB report may fall into the wrong hands. A DSMB Charter will further describe procedures and membership.

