6.8. Multiple Comparisons/Multiplicity

There is only one primary outcome measure. The study utilizes a group-sequential design to control the overall type I error rate while allowing for formal interim analyses of the primary outcome measure (as described in Section 6.6 and Section 8.1). For the primary analysis of time to recovery, the stratified log-rank test will be performed in the efficacy analysis populations including all three severity strata and the p-value will be reported. If the resulting p-value is significant, then the analysis that excludes subjects in the severity = 6 strata will include the stratified log-rank test and the p-value will be reported. If the p-value from the primary analysis (including all three strata) is not significant, then the stratified log-rank test will not be performed for the analysis that excludes the severity = 6 strata and no p-value will be reported.

Likewise, the p-value for the analyses of the following will only be reported if the p-value from the primary analysis of time to recovery (including all three strata) is significant:

- The proportional odds model for the key secondary endpoint of clinical status score at Study Visit Day 15;
- Time to death through Day 15 (baseline ordinal score 4 or 5);
- Time to death through Day 29 (baseline ordinal score 4 or 5).

There is no planned adjustment for multiple comparisons in any secondary or exploratory analyses.

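### At the final look, SAP 8.1.1 reports the primary result as fixed-sample statistics at 5% although alpha was spent at the interim, and SAP 6.8 does not say which criterion makes the result significant

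*SAP*

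**What the plan says.** SAP 6.6.3 plans one interim efficacy look: "An interim efficacy analysis will be conducted after approximately 50% of total information has been reached". ACTT-3 Appendix C, section 9.4.7.2, agrees, listing 50% and 100% of information. An O'Brien-Fleming-type Lan-DeMets spending function is used "to monitor the primary endpoint using an overall two-sided type-I error rate of 0.05", and "two one sided boundaries are constructed at level 0.025 using the spending function" given in that section.

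SAP 8.1.1 then treats the primary result in three ways:

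- It gives PROC SEQTEST code that can be used to obtain the final-look bounds, updated for the information actually seen at the interim, and to compare the log-rank statistic with them.
- If the trial stops at the interim, then for the p-value, hazard ratio and confidence interval of both the early and the final analysis sets, "stage-wise ordering of the sample space will be used".
- Otherwise: "If the trial is not stopped early, then the fixed sample estimates of the statistics using an alpha level of 5% will be computed".

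Two other sections depend on this. SAP 6.1 says that "for the primary analysis, the confidence level will take into account the group-sequential design of the trial" and points to 6.6 and 8.1. SAP 6.8 invokes the group-sequential design as its control of type I error and then sets a gate: "If the resulting p-value is significant, then the analysis that excludes subjects in the severity = 6 strata" receives a test and a reported p-value. The same condition governs the p-values for Day 15 clinical status and for mortality through Days 15 and 29 in baseline scores 4 and 5. Neither 6.8 nor the programming note to Table 10 gives a numerical threshold.

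**The concern.** Once alpha has been spent at an interim look, a final statistic cannot be read against 1.96 if the overall error is to remain 0.05. The chance of having crossed earlier must be counted in the bound, the p-value and the interval. SAP 8.1.1 provides a bound that counts it, then reports a p-value, estimate and interval that do not. A final |Z| of 1.965 would fail the SEQTEST bound and still be printed as p=0.049.

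The programmer and the reader would then have two answers to whether the primary analysis succeeded. That answer also decides whether four further p-values are reported: recovery in scores 4 and 5, Day 15 status, and mortality at two time points.

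**Working it through.** **Inputs.** Two-sided alpha 0.05, the spending function and one look at about 50% information with t = r/723 (SAP 6.6.3). 723 recoveries for a ratio of 1.25 at 85% power, and enrolment until 831 recoveries (SAP 5). 1:1 allocation (Appendix C, 6.1).

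**The plan's own figure.** E = 4(1.96 + z_β)²/(ln 1.25)². With z_β rounded to 1.04 this is 4 × 9.00/0.04979 = 723, so the SAP's number is reproduced. Fixed-design power at 723 is 85.1%.

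**Step 1: alpha spent at the interim.** At t = 0.5, 2.241/√0.5 = 3.169. The function spends 2[1 − Φ(3.169)] = 0.00153 per side, or 0.0031 two-sided. The interim bound is |Z1| ≥ 2.96.

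**Step 2: final bound.** Take (Z1, Z2) as bivariate normal with correlation √(I1/I2). Solve P(|Z1| ≥ 2.962 or |Z2| ≥ b) = 0.05 for b, then compute the same probability with b = 1.96.

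| Interim / final recoveries | Correlation | Correct final bound (nominal p) | Overall alpha if 1.96 is used |
|---|---|---|---|
| 361.5 / 723 | √0.500 = 0.707 | 1.969 (0.0490) | 0.0510 |
| 361.5 / 831 | √0.435 = 0.660 | 1.971 (0.0487) | 0.0512 |

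If the interim were instead taken at half of 831 (415.5 recoveries), t = 415.5/723 = 0.575. Then 0.0062 is spent, the interim bound is 2.735, the final bound is 1.982 and overall alpha with 1.96 is 0.0525. With the final look at full information and the single interim anywhere from t = 0.33 to 0.70, overall alpha with 1.96 runs from 0.0501 to 0.0542.

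**Step 3: reported p-values at the final look.** The one-sided stage-wise p is P(Z1 ≥ 2.962) + P(|Z1| < 2.962, Z2 ≥ z), doubled for two sides (361.5 / 723 recoveries).

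| Final z | Fixed-sample p | Stage-wise p |
|---|---|---|
| 1.965 | 0.0494 | 0.0504 |
| 2.2 | 0.0278 | 0.0292 |
| 2.6 | 0.0093 | 0.0113 |

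Only the first row changes a decision. The other two show that the reported figure is too small even where the conclusion is unaffected.

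**Step 4: coverage.** In 4 million simulated trials, fixed-sample 95% intervals, taken over both early and late stopping, cover 94.9% of the time at a true ratio of 1 and 94.7% at 1.25.

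**Step 5: stopping at the interim.** No look precedes the first, so stage-wise p is simply P(Z1 ≥ z1). For z1 = 3.1 both methods give 0.0019, and the estimate and interval coincide too. This holds for the early analysis set. If recoveries accrue after the stop, the final set can differ. With an assumed overrun to 500 recoveries, treated as a second stage, and Z = 3.0, stage-wise p is 0.0047 and fixed-sample p is 0.0027.

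**Step 6: cost of the correct bound.** With bounds 2.963 and 1.969, power at 723 recoveries and a ratio of 1.25 is 84.9%.

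**The case against.** The best defence is that 8.1.1 already contains the right decision rule. The SEQTEST step computes final bounds and compares the statistic with them, and 6.8 names the group-sequential design as its error control just before it uses the word significant. On that reading the fixed-sample sentence concerns only what is reported, significance means crossing the bound, and overall alpha is exactly 0.05. This is a fair reading and may be the intended one. But the code is introduced only as something that can be used, 6.8 speaks of a p-value rather than a bound, and the p-value that 8.1.1 produces at the final look is the unadjusted one. Even on this reading, the reported interval does not match the promise in 6.1.

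A reader might go further and infer that the plan has the adjustment backwards: applied only on early stopping, where it does nothing, and dropped at the end. The documents do not support that. An adjusted bound is supplied for the final look. Stage-wise ordering is also assigned to the final analysis set after an early stop, and enrolment does not pause for DSMB reviews (Protocol 10.1.6.2), so overrun data are plausible and would make the adjustment matter.

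It is also true that the effect is small: about 0.001 of alpha and a band of roughly 0.01 in Z.

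**Conclusion.** The SAP gives two incompatible treatments of the primary result when the trial reaches its final look, and 6.8 does not choose between them. If fixed-sample p<0.05 is the criterion, overall two-sided alpha is 0.0510, or 0.0512 with the final look at 831 recoveries, and both the primary decision and the gate differ for a final |Z| between 1.960 and about 1.97. If the SEQTEST bound is the criterion, alpha is held and the defect is confined to the reported p-value, estimate and interval. It would be wrong to state flatly that the trial fails to control type I error, because that depends on a reading that the text leaves open.

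The figures assume a single efficacy look at t = 0.5, as in the SAP and Appendix C. The main protocol (10.1.6.2) also mentions formal safety and efficacy reviews about every 200 recoveries. If alpha were spent at those, the final bound would have to be recomputed. The point is minor in size but worth correcting, because it concerns the primary decision rule and costs almost nothing.

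**What to change.** - In 8.1.1 and 6.8, state that primary significance, including the gate for the secondary p-values, means crossing the final Lan-DeMets bound: about 1.97, nominal p about 0.049, recomputed from the information actually observed. Carry this into the Table 10 programming note.
- Replace the fixed-sample sentence in 8.1.1 so that, when the trial continues to the final look, the stage-wise-ordering p-value, median-unbiased hazard ratio and interval are reported. This also brings 8.1.1 into line with 6.1.
- Reconcile t = r/723 with a final look at 831 recoveries, so that the bound is computed on one information scale.

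The cost is SAP wording. The SEQTEST step is already in the plan. The final p-value becomes slightly less favourable, and power at 723 recoveries is 84.9% against 85.1% for a fixed design.
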